I have read and understand this protocol, and will comply with the requirements for obtaining informed consent from all study subjects prior to initiating any protocol-specific procedures, understand and abide by the requirements for maintenance of source documentation, and provide assurance that this study will be conducted according to all requirements as defined in this protocol, clinical study agreement, Code of Federal Regulation, and all applicable regulatory requirements.

I also agree that persons debarred from conducting or working on clinical studies by any court or regulatory agency will not be allowed to conduct or work on this study. I will immediately disclose it in writing to the Sponsor if any person who is involved in the study is debarred, or if any proceeding for debarment is pending, or, to the best of my knowledge, threatened.

This document contains confidential information of the Sponsor, which must not be disclosed to anyone other than the recipient study staff and members of the IRB/EC. I agree to ensure that this information will not be used for any purpose other than the evaluation or conduct of the clinical investigation without the prior written consent of the Sponsor.

Principal Investigator

[name]., Ph.D.

Director

Center for Clinical and Cosmetic Research
[name]
[contact]
Ph. [contact]

Date

PROTOCOL SYNOPSIS

Protocol Title:	A Double-Blind, Pilot Study to Evaluate the Efficacy and Safety of Topical AFX 5931 in the Treatment of Mild to Moderate Hand Dermatitis
Protocol Number:	CCCR 08-2018
Phase/Type:	Pilot - Investigator Initiated Trial (IIT)
Principal Investigator:	[name]., Ph.D. Center for Clinical and Cosmetic Research [name]
Study Center(s):	One (1) study center in the United States: Center for Clinical and Cosmetic Research [name]
Objectives:	
Primary Objective:
 
 1. To measure the efficacy of topical AFX 5931 in the treatment of mild to moderate hand dermatitis in subjects 12 years of age and older 
Secondary Objective:
 
 2. To measure the tolerability and safety of topical AFX 5931 in the treatment of mild to moderate hand dermatitis in subjects 12 years of age and older
Study Design:	This is a double-blind, pilot study with 20 subjects to determine the tolerability and efficacy of topical AFX 5931 in the treatment of mild to moderate hand dermatitis. Subjects are screened up to 30 days before the baseline visit. Subjects who meet the eligibility criteria may qualify for the study. Subjects will be randomized in a 3:1 ratio to receive either the active or vehicle medication. 15 subjects will receive the active, therapeutic product and 5 subjects will receive the inactive, vehicle product. Subjects will complete 4 study visits according to the following 4-week timeline: Day [-30] – [-1] (Screening), Day 0 (Baseline), Day 14 (Follow-Up), Day 28 (Follow-up ET EOS). At Visit 2, IP will be dispensed and baseline readings of efficacy as well as safety/tolerability assessments will be obtained prior to application of the IP. Subjects will apply IP twice daily and compliance will be monitored by periodically reviewing the subject diary. The evaluations that will be used to measure efficacy of the product will be the Investigator's Global Assessment and Hand Eczema Severity Index. The Subject's Local Dermal Tolerability Assessment and Local Skin Reaction Assessment will be used throughout the course of the study to evaluate tolerability. Additionally, the actions that will be taken to evaluate safety will be the monitoring of adverse events, vital signs, and changes in concomitant medications. Digital photographs will be taken at each visit (excluding Visit 3).

Inclusion Criteria:	
 1. Subject is a male or non-pregnant female, 12 years of age and older. 2. Subject is willing and able to provide written informed consent for the study. 3. Subject is willing and able to apply the investigational product as directed, comply with study instructions and commit to all follow-up visits for the duration of the study. 4. Subject has clinical diagnosis of mild to moderate hand dermatitis for at least 3 months. 5. Subject has a baseline Investigator's Global Assessment (IGA) score of 2 or 3 (disease severity of mild or moderate). 6. Subject is in good general health and free of any disease state or physical condition that might impair evaluation of hand dermatitis or which, in the investigator's opinion, exposes the subject to an unacceptable risk by study participation. 7. Women of childbearing potential (WOCBP) must use an effective method of birth control or must be post-menopausal or surgically sterile. Women of childbearing potential (WOCBP) must have a negative urine pregnancy test (UPT) at Baseline.
Exclusion Criteria:	
 1. Subject is pregnant, lactating, or is planning to become pregnant during the study. 2. Subject is currently enrolled in an investigational drug or device study. 3. Subject has used an investigational drug or investigational device treatment within 30 days prior to Visit 2/Baseline. 4. Subject has active cutaneous bacterial or viral infection in any treatment area (clinically infected hand dermatitis) at Visit 2/Baseline. 5. Subject has used any of the following therapies within 30 days prior to Visit 2/Baseline: 
 • Systemic corticosteroids (oral and injectable [intravenous and intramuscular]) (Intranasal and Inhalational steroids are allowed if use is kept constant during the study) • UVA/UVB therapy • PUVA (psoralen plus ultraviolet A) therapy • Immunomodulators or immunosuppressive therapies • Interferon • Cytotoxic drugs (e.g., methotrexate, cyclophosphamide, azathioprine) • Oral retinoids 6. Subject has used any of the following therapies within 14 days prior to Visit 2/Baseline: 
 • Systemic antibiotics • Topical calcipotriene or other topical vitamin D preparations 7. Subject has used any of the following therapies within 7 days prior to Visit 2/Baseline: 
 • Topical and oral antihistamines • Topical antibiotics • Topical corticosteroids • Topical antifungals 8. Subject has a history of sensitivity to any of the ingredients in the investigational product.

	
9. Subject is known to be noncompliant or is unlikely to comply with the requirements of the study protocol (e.g., due to alcoholism, drug dependency, mental incapacity) in the opinion of the investigator.

Investigational Products:	
Medication Name:
 
 1. Active Treatment: Topical AFX 5931 
 - A medication combining a series of small, potent anti-inflammatory molecules that down-regulate the CCL5/CCL2 pro-inflammatory pathway 2. Vehicle
Patient Population:	
 - 20 healthy, adult male or non-pregnant female subjects - 12 years of age and older
Safety Endpoints:	
Safety/tolerability endpoints are monitored by members of the study staff. They include the following:
 
 - Changes in local skin reaction - Changes in AEs and serious adverse events (SAEs) - Changes in vital signs and physical examinations - Changes in concomitant procedures/medications - Presence of signs/symptoms of irritation of the skin.
Statistical Methods:	
 - All analyses of the pooled individual patient data will be performed with the use of SPSS software using a two-way Chi-square test analysis, t-tests, odds ratios, and analysis of variance (ANOVA).
Assessments:	
 - Hand Eczema Severity Index 
 o Investigator-rated: clinical evaluation of both the extent and intensity of hand dermatitis 
 ▪ Clinical signs: erythema, infiltration/papulation, vesicles, figures, scaling, and edema ▪ Locations: fingertips, fingers (excluding tips), palms of hands, backs of hands, wrists ▪ Extent is graded on a visual 5-point scale ▪ Intensity is graded on a visual 4-point scale - Local Skin Reaction Assessment 
 o Investigator-rated: clinical grading score of erythema, induration/papulation, and lichenification 
 ▪ Each parameter is graded on a visual 4-point scale - Subject's Local Dermal Tolerability Assessment: 
 o Subject-Rated: clinical grading score of pruritus 
 ▪ Each parameter is graded on a visual 4-point scale - See assessments reference at end
Randomization:	
 - The subjects will be randomized to receive either the active or control medication based on a 3:1 randomization scheme - Out of 20 total subjects, 15 will receive the active treatment while 5 will receive the vehicle
Photography:	
 - Digital photographs will be taken at proximal and distal views of the dorsal as well as palmar surfaces of the hand

3 OBJECTIVES

3.1 Primary and Secondary Objectives

Primary Objective:

1. To measure the efficacy of topical AFX 5931 in the treatment of mild to moderate hand dermatitis in subjects 12 years of age or older
 - a. Assessed via Hand Eczema Severity Index
 - b. Assessed via Investigator's Global Assessment

Secondary Objective:

2. To measure the tolerability and safety of topical AFXC 5931 in the treatment of mild to moderate hand dermatitis in subjects 12 years of age or older
 - a. Assessed via Subject's Local Dermal Tolerability Assessment
 - b. Assessed via Local Skin Reaction Assessment
 - c. Assessed via changes in adverse events or concomitant medications

3.2 Overview

This is a double-blind, pilot study with 20 subjects to determine the tolerability and efficacy of topical AFX 5931 in the treatment of mild to moderate hand dermatitis. Subjects are screened up to 30 days before the baseline visit. Subjects who meet the eligibility criteria may qualify for the study. Subjects will be randomized in a 3:1 ratio to receive either the active or control medication, in which 15 subjects will receive the active, therapeutic product and 5 subjects will receive the inactive, vehicle product. Subjects will complete 4 study visits according to the following 4-week timeline: Day [-30] – [-1] (Screening), Day 0 (Baseline), Day 14 (Telephone Call), Day 28 (Follow-up | ET | EOS). At Visit 2, IP will be dispensed and baseline readings of efficacy and safety/tolerability assessments will be obtained prior to application of the IP. Subjects will apply IP twice daily and compliance will be monitored by reviewing the subject diary periodically throughout the study. The assessments that will be used to evaluate efficacy of the product will be the Hand Eczema Severity Index and Investigator's Global Assessment. The Subject's Local Dermal Tolerability Assessment and Local Skin Reaction Assessment will be used throughout the course of the study to evaluate tolerability. Additionally, the actions that will be taken to evaluate safety will be the monitoring of any adverse events or concomitant medications. Digital photographs will be taken at each visit (excluding Visit 3).

4 STUDY POPULATION

4.1 Inclusion Criteria

Subjects who meet all of the following criteria are eligible for this study:

1. Subject is a male or non-pregnant female, 12 years of age and older.
2. Subject is willing and able to provide written informed consent for the study.
3. Subject is willing and able to apply the investigational product as directed, comply with study instructions and commit to all follow-up visits for the duration of the study.
4. Subject has clinical diagnosis of mild to moderate hand dermatitis for at least 3 months.
5. Subject has a baseline Investigator's Global Assessment (IGA) score of 2 or 3 (disease severity of mild or moderate).
6. Subject is in good general health and free of any disease state or physical condition that might impair evaluation of hand dermatitis or which, in the investigator's opinion, exposes the subject to an unacceptable risk by study participation.
7. Women of childbearing potential (WOCBP) must use an effective method of birth control or must be post-menopausal or surgically sterile. Women of childbearing potential (WOCBP) must have a negative urine pregnancy test (UPT) at Baseline.

4.2 Exclusion Criteria

Subjects who meet any of the following criteria are not eligible for this study:

1. Subject is pregnant, lactating, or is planning to become pregnant during the study.
2. Subject is currently enrolled in an investigational drug or device study.
3. Subject has used an investigational drug or investigational device treatment within 30 days prior to Visit 2/Baseline.
4. Subject has active cutaneous bacterial or viral infection in any treatment area (clinically infected hand dermatitis) at Visit 2/Baseline.
5. Subject has used any of the following therapies within 30 days prior to Visit 2/Baseline:
 - Systemic corticosteroids (oral and injectable [intravenous and intramuscular]) (Intranasal and Inhalational steroids are allowed if use is kept constant during the study)
 - Immunomodulators or immunosuppressive therapies
 - Interferon
 - Cytotoxic drugs (e.g., methotrexate, cyclophosphamide, azathioprine)
 - Oral retinoids
6. Subject has used any of the following therapies within 14 days prior to Visit 2/Baseline:
 - Systemic antibiotics
 - Topical calcipotriene or other topical vitamin D preparations
 - Topical retinoids
7. Subject has used any of the following therapies within 7 days prior to Visit 2/Baseline:
 - Topical and oral antihistamines
 - Topical antibiotics
 - Topical corticosteroids
 - Topical antifungals
 - Other topical drug products
8. Subject has a history of sensitivity to any of the ingredients in the investigational product.

9. Subject is known to be noncompliant or is unlikely to comply with the requirements of the study protocol (e.g., due to alcoholism, drug dependency, mental incapacity) in the opinion of the investigator.

4.3 Withdrawal and Replacement of Patients

Patients who withdraw consent must be withdrawn from the study. No justification for such a decision is required. Patients must be withdrawn from the study if the investigator considers it in the best interest of the patient that he/she be withdrawn. Patient must notify the principal investigator in writing at the time of their decision. The reasons for withdrawal must be recorded, if available, on the case report form (CRF) and in the patient's medical records. If possible, a complete, final examination should be performed on all patients who withdraw from the study. Patients who are withdrawn will not be replaced.

4.4 Patient Identification

All patients enrolled must be identifiable throughout the study. The investigator will maintain a personal list of patient numbers and patient names to enable records to be found at a later date.

Subjects will receive a patient number as detailed in a separate document located in the investigator's file. Patients who terminate their study participation for any reason after signing the consent form, regardless of whether study medication was taken or not, will retain their patient identification number. In that case, the next patient identification number and bottle in the sequence are to be used. The following patient is given the next patient identification number. Screen failures will not be assigned a patient identification number. Screen failures are not to interrupt the patient identification schema for the enrolled subjects.

5 STUDY MEDICATION

5.1 Identity

Trade Name:	AFX 5931
Manufacturer:	Afecta Pharmaceuticals

5.2 Maintaining the Blind

The subjects will be randomized to receive one of two treatments (active vs. control) in a 3:1 ratio. Thus, out of the total 20 subjects, 15 subjects will receive the active “AFX 5931” medication while 5 subjects will receive the vehicle product. Separate study staff members are assigned to administer the study medication versus conduct study evaluations.

5.3 Administration

The subject will be instructed on how to apply the IP independently for use throughout the rest of the study at the baseline visit (Visit 2).

5.4 Compliance

Subject compliance is based on attending every required study visit and completing applications of the medication twice daily starting from the baseline visit. Subjects will be required to qualify for the study honestly and return for all study visits. Subject will be required to fill out a record of IP applications on a subject diary, which must be filled out throughout the study. Any missing of visits or doses may qualify for withdrawal from the study under the Principal Investigator’s discretion.

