7.2 Statistical Methods

7.2.1 General Statistical Methods

All data collected during the study will be presented in data listings. Summary tables and analyses will be based on the following analysis populations:

Safety population:	All enrolled subjects who received study treatment.
Intention-to-treat (ITT) population:	All enrolled subjects, regardless of whether they received study treatment.
Per protocol (PP) population:	All subjects in the ITT population for whom no major protocol violations occurred.

The primary population for analyses of efficacy data will be ITT population. A supportive analysis will be presented for the PP population if this is significantly different from the ITT population. The assessment of safety will be based on the safety population.

Continuous data will be summarized by treatment group using descriptive statistics (number, mean, median, standard deviation, minimum, and maximum). Categorical data will be summarized by treatment group using frequency tables (frequencies and percentages). Ninety-five percent confidence intervals will be constructed for proportions of successes.

Statistical tests will be used for analysis. The analysis will be 2-sided and conducted at the 0.05 significance level. An analysis of means using an independent samples t-test and ANOVA will be used. Primary analysis will be completed with the help of a chi-square analysis and assessment of relative risk and odds ratios.

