7.2.2 Sample Size

The total sample size needed is 20 subjects that are 12 years of age and older. Each subject will be randomized in a 3:1 ratio to receive either the active (15 subjects) or vehicle (5 subjects) product throughout the study. Endpoints will be evaluated using a 2-sided Chi-square test and t-test at the 0.05 significance level.

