7.3 Source Documents

The full dataset will be collected for all subjects enrolled. All required data for this study will be collected on paper source document worksheets. The collected data will be entered into a validated database. Database lock will occur once quality assurance procedures have been completed.

Source data is all information, original records of clinical findings, observations, or other activities in a clinical trial necessary for the reconstruction and evaluation of the trial. Source data are contained in source documents. Examples of source documents include hospital records, office charts, memoranda, evaluation checklists, photographs, and subject files.

All procedures for the handling and analysis of data will be conducted using good computing practices meeting USFDA guidelines for the handling and analysis of data for clinical trials.

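### Section 5.4 permits discretionary withdrawal from the whole study for any missed dose or visit, so Day 28 HECSI and IGA values may be avoidably lost from the primary ITT analysis

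*Combined protocol and SAP*

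**What the plan says.** Section 5.4 (Compliance) sets a strict standard: "Subject compliance is based on attending every required study visit and completing applications of the medication twice daily starting from the baseline visit". Its last sentence attaches a consequence: "Any missing of visits or doses may qualify for withdrawal from the study", left to the Principal Investigator's discretion. No number of missed doses or visits is given, and the consequence is leaving the study, not merely stopping product.

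Section 4.3 already provides for withdrawal of consent and for withdrawal in the patient's best interest, so Section 5.4 adds a third ground based on adherence alone. Section 4.3 also states "Patients who are withdrawn will not be replaced", and on exit data "If possible, a complete, final examination should be performed on all patients who withdraw from the study". Section 6.4.4 labels Visit 4 as the early-termination visit as well as Day 28, with HECSI and IGA completed there.

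On analysis, Section 7.2.1 makes ITT, meaning all enrolled subjects whether treated or not, the primary efficacy population. It defines the per-protocol (PP) population as "All subjects in the ITT population for whom no major protocol violations occurred" and presents that analysis only if it differs significantly from ITT. Section 7.2.4 leaves missing data blank. Section 7.2.2 fixes the arms: "Each subject will be randomized in a 3:1 ratio to receive either the active (15 subjects) or vehicle (5 subjects) product throughout the study".

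**The concern.** Missing a dose happens after randomisation and can depend on treatment: a subject on vehicle may see no benefit, and a subject on active may be irritated or may clear early and stop bothering. If such subjects are taken out of follow-up, the values that remain come increasingly from adherers, and the ITT result moves towards an adherers-only result. The direction of any bias cannot be predicted.

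The loss would be avoidable, because the visits at which these subjects would be scored are already in the schedule. It would also be costly in this trial, since each vehicle subject is one fifth of the arm and cannot be replaced.

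**Working it through.** **Planned numbers.** Section 7.2.2 gives 20 subjects at 3:1. 20 × 3/4 = 15 and 20 × 1/4 = 5, which agrees with the stated split. The documents give no effect size, SD, response rate, power or dropout rate, so the total of 20 cannot itself be reproduced.

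**From withdrawal to a lost value.**

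1. Section 5.4 permits withdrawal from the study after any missed dose or visit.
2. Section 4.3 does not replace the subject and secures an exit examination only where possible.
3. No section says that a withdrawn subject is followed to Day 28, or how an early-termination score enters the Day 28 analysis.
4. Section 7.2.4 leaves the gap blank. The tests named in Sections 7.2.1 and 7.2.2 (chi-square, t-test, ANOVA), applied at a visit, cannot use a subject with no value at that visit.

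The subject is therefore in the ITT population by definition but may contribute nothing to the Day 28 comparison.

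**How many subjects the dose trigger could reach.** Twice daily for 28 days is 2 × 28 = 56 applications. With an assumed per-dose miss rate p, independent between doses, the probability of at least one miss is 1 − (1 − p)^56. The last column is that probability times 20.

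| Assumed p | Probability of at least one missed dose | Eligible of 20 |
|---|---|---|
| 0.5% | 24.5% | 4.9 |
| 1% | 43.0% | 8.6 |
| 2% | 67.7% | 13.5 |
| 5% | 94.3% | 18.9 |

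At 2%, that is 15 × 0.677 = 10.2 active and 5 × 0.677 = 3.4 vehicle subjects. These are subjects who could be withdrawn under the rule. The miss rates are assumptions, and missed visits are not counted.

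**Cost of losing vehicle subjects (a separate illustration, not linked to the miss rates).** With a common SD, the standard error of the mean difference is SD × √(1/15 + 1/n), where n is the number of vehicle subjects with data and all 15 active subjects are kept. The detectable difference is for 80% power, two-sided 0.05, from the noncentral t distribution.

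| n | SE / SD | Increase in SE | Detectable difference |
|---|---|---|---|
| 5 | √(0.0667 + 0.2000) = 0.516 | none | 1.53 SD |
| 4 | √(0.0667 + 0.2500) = 0.563 | 0.563/0.516 − 1 = 9% | 1.67 SD |
| 3 | √(0.0667 + 0.3333) = 0.632 | 0.632/0.516 − 1 = 22% | 1.89 SD |

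**Chance of losing vehicle subjects.** If each vehicle subject had an assumed withdrawal probability w, the chance of losing at least one of five is 1 − (1 − w)^5: 23% at w = 5%, 41% at 10% and 67% at 20%.

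**Possible size of bias.** As an extreme case, if the one vehicle subject lost were always the most extreme on one side, the vehicle mean would shift by about 0.29 SD (simulation with normal data). Nothing in the plan implies selection that strong.

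**The case against.** The strongest reply is that several provisions soften the rule. Withdrawal is permitted, not required. Section 4.3 asks for a final examination where possible, and Visit 4 doubles as the early-termination visit, so a withdrawn subject may still give an exit score. Sections 4.3 and 7.2.5 have reasons for withdrawal or discontinuation recorded and reported, so discretionary removals would be visible. The study is double-blind, and Section 5.2 separates the staff who administer medication from those who evaluate. It is also a 20-subject pilot with no stated power target. All of this stands and limits the point. It does not dispose of it: an exit score is neither guaranteed nor assigned a role in the analysis, the blind does not stop response or irritation from causing missed doses, and Section 5.2 does not say that the withdrawal decision is kept apart from evaluation.

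Four stronger readings are tempting but unsupported:

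- **That Section 5.4 contradicts the ITT definition or the data-collection statement.** A withdrawn subject remains an enrolled subject and so remains in ITT. The sentence "The full dataset will be collected for all subjects enrolled" sits under Source Documents (Section 7.3) and concerns data capture, not follow-up after withdrawal. Both are in tension with the rule, and neither is contradicted by it.
- **That a quarter to nearly all subjects would be lost.** The percentages count eligibility under assumed miss rates. The documents do not say how often the discretion would be used.
- **That the investigator could remove subjects knowing their arm.** The blind speaks against this. The remaining route is indirect, through reasons for non-adherence that differ by arm.
- **That the PP analysis already deals with poor adherence.** Section 7.2.1 does not define a major violation, does not say when that is decided, and presents the PP result only conditionally.

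**Conclusion.** The point holds as a preventable weakness in a stated rule. Section 5.4 gives an unguided power to end a randomised subject's participation for any lapse in adherence. Combined with no replacement, a conditional exit examination and blank missing data, it can cost the primary ITT analysis outcome values that the existing visit schedule could have supplied.

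The eligibility figures of 25% to 94% rest on about 56 independent applications and assumed miss rates of 0.5% to 5%. They are an upper bound on withdrawal for missed doses at those rates. The 9% and 22% increases in standard error assume that 1 or 2 vehicle subjects are lost and no active subject is. The actual loss depends on how the discretion is used, which is unknown, and the direction of any bias is undetermined. Confidence is medium. The change is worth making because it is cheap, not because large losses have been shown to be likely.

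**What to change.** Replace the last sentence of Section 5.4 with:

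> Missed doses or visits are recorded as protocol deviations and are not in themselves a reason for withdrawal from the study. Subjects who miss doses or a visit, or who stop applying product, are asked to attend the remaining scheduled visits, where HECSI, IGA, local skin reaction and itch are scored, unless they withdraw consent or are withdrawn under 4.3.

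In Section 7.2.1, state which non-adherence counts as a major protocol violation for the PP population, require that this be decided before unblinding, and present the PP analysis whether or not it differs from ITT.

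Consent and best-interest withdrawal in Section 4.3 are unchanged, and nothing here says when treatment should stop.

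The cost is one replacement passage in Section 5.4 and a short definition in Section 7.2.1, using visits already in the Section 6.3 schedule. The downside is that poorly adherent subjects stay in ITT and may slightly dilute the effect. A visit that is missed still yields no score. How an early-termination score enters the Day 28 analysis remains to be specified; this change makes the question arise less often but does not answer it.
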